5.6 Data Review for Statistical Purposes

A review of the data has been anticipated through the data review process led by data management before database lock. This review of the data included a statistical review.

5.7 Changes in the Conduct of the Trial or Planned Analyses

In the last version of the protocol (version 4 approved on 16^{th} February 2022), the D29 visit is to be performed with a time window of +3 days; a blood sample BL0003 has to be taken at the D29 visit.

However, the timing for the Phase II non-inferiority VYF02 study has been complicated by COVID epidemic waves and vaccination campaigns; when non-COVID work was resuming at Investigational sites, these studies were competing against other studies. As a direct consequence, the enrolments were delayed and longer than expected. Considering that the planned sample size was likely to be not reached, the Applicant worked on a mitigation plan based on the number of evaluable subjects (derived from the attrition rate used for the statistical hypotheses) consisting of extending the time window of the D29 post-vaccination visit (initial defined as D29 + 3 days) with a proposal to extend up to D29 + 6 days, as the immune responses should not be impacted by this extension. The analyses with a revised time window for the D29 visit +6days will be presented as the primary analysis of the non-inferiority of the antibody response in terms of seroconversion rates 28 days after vaccine administration of one dose of vYF (administered on D01) compared to the antibody response after one dose of the YF-VAX control vaccine (administered on D01) in YF-naïve participants. If the primary objective is reached, in secondary objective, the originally planned analysis of the non-inferiority of the antibody response on D29 with a time window of +3 days will be presented too and completed with a descriptive analysis in terms of seroconversion, seroprotection GMT and GMTR.

Moreover, by contrast to the analyses defined in the protocol, the first interim analysis will be performed on safety and immunogenicity data gathered from D01 to D29 (instead of M6 for safety data).

6 References List

- Eduardo J. M. Nascimento, Matthew I. Bonaparte, Ping Luo, Timothy S. Vincent, Branda Hu, James K. George, Germán Áñez, Fernando Noriega, Lingyi Zheng and James W. Huleatt. "Use of a Blockade-of-Binding ELISA and Microneutralization Assay to Evaluate Zika Virus Serostatus in Dengue-Endemic Areas" Am. J. Trop. Med. Hyg., 101:708-715, 2019.
- 2 Newcombe R.G., Two-sided confidence intervals for the single proportion: comparison of seven methods, Statistics in Medicine, (1998) 17, 857-872

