2.3.2 Benefits from Study Participation

This study is experimental research and there is no guarantee that participants enrolled in VYF02 will get any benefit.

vYF is a next-generation live-attenuated YF vaccine produced on serum-free Vero cells without any component of animal origin. vYF has been developed to induce a life-long immunity against YF and to be at least as immunogenic as other licensed YF-17D vaccines and well-tolerated.

Participants enrolled in VYF02 will be followed up yearly up to 5 years post vaccine administration to assess the maintenance over time of the immune response.

It is expected that participants enrolled in VYF02 will be protected against YF, which means that both the new investigational vaccine as well as the current licensed YF-VAX vaccine, elicit a safe, protecting, and long-lasting immune response.

International Certificate of Vaccination or Prophylaxis for YF Vaccination

At the end of the first interim analysis and at the end of the study, the Investigators will be provided with individual listings detailing for each participant the vaccine group assignment and the neutralizing antibody titers at the successive time points. Participants are responsible for contacting the study site to find out which study group they were assigned to and which vaccine they received.

Participants enrolled in the YF-VAX group can be provided by the investigational site with the ICVP for YF vaccination, while those enrolled in a vYF group would be informed that they need to obtain a licensed YF vaccine prior to travel to endemic areas.

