9.5 Interim Analyses

Interim Analyses

Six statistical analyses will be performed on data obtained from all participants.

The first interim analysis will be performed on the immunogenicity results obtained up to the D29 visit and safety data obtained up to the 6-month follow-up visit, then the successive interim analyses will be performed on data collected up to Y1 visit and not yet analyzed, then every year on the data gathered at each yearly visit up to 4 years after YF vaccine administration; these

results will be presented in an interim clinical study report (CSR) (immunogenicity data up to D29 and safety data up to M6) or CSR addendum (up to Y4).

Final Analysis

The final analysis will be performed at the end of the follow-up (5 years after YF vaccine injection).

[figure not shown]
The SAP will describe the planned interim analyses in greater detail.

Ongoing Safety Surveillance

This study will not include an early safety data review. However, participant safety will be continuously monitored by the Sponsor's internal safety review committee: Safety Management Team (SMT) which includes safety signal detection at any time during the study.

This SMT led by the Global Safety Officer (GSO) includes core representatives from the Global Pharmacovigilance (GPV) Department and from the Clinical Department. The SMT is empowered to recommend a pause in recruitment while it investigates any potential signal or concern.

The enrollment will be paused if one of the following pausing/halting criteria that could potentially constitute an unreasonable and significant risk for study participants occurs:

The study can be resumed if investigations conclude that there is no unreasonable and significant risk for study participants.

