⁺⁺⁺ The first interim analysis is on safety and immunogenicity up to D29 only.

4 Endpoints and Assessment Methods

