5.4 Interim / Preliminary Analysis

Six statistical analyses will be performed on data obtained from all participants.

The first interim analysis will be performed on the immunogenicity results obtained up to D29 visit and safety data obtained up to the 6-month follow-up visit with all available data collected, cleaned and locked. This planned analysis will require the unblinding of data. Once the interim database lock has been conducted, the trial statistician will break the blind and will conduct the statistical analysis.

Then the successive interim analyses will be performed on data collected up to Y1 visit and not yet analyzed, then every year on the data gathered at each yearly visit up to 4 years after YF vaccine administration; these results will be presented in an interim clinical study report (CSR) (immunogenicity data up to D29 and safety data up to M6) or CSR addendum (up to Y4).

Final statistical analysis will be performed at the end of the follow-up (5 years after YF vaccine injection).

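### The SAP gives two cut-offs for the first interim analysis, and the D29 one allows Investigators to receive vaccine assignments before later-enrolled participants finish 6-month safety follow-up

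*SAP*

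**What the plan says.** Cut-off of the first interim analysis:

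- Protocol 9.5: immunogenicity to D29 and "safety data obtained up to the 6-month follow-up visit".
- SAP 5.4: the same, with "safety data obtained up to the 6-month follow-up visit with all available data collected, cleaned and locked". Its description of the interim study report repeats this: "immunogenicity data up to D29 and safety data up to M6".
- SAP Table 3.2 footnote (section 3.2): "The first interim analysis is on safety and immunogenicity up to D29 only".
- SAP 5.7, declared as a departure from the protocol: "the first interim analysis will be performed on safety and immunogenicity data gathered from D01 to D29 (instead of M6 for safety data".

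Unblinding at that point:

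- SAP 5.4: "Once the interim database lock has been conducted, the trial statistician will break the blind and will conduct the statistical analysis".
- Protocol 2.3.2: "At the end of the first interim analysis and at the end of the study, the Investigators will be provided with individual listings". These show which vaccine each person received, together with that person's titers. Participants may then contact the site to learn what they received.

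Safety data still being collected: protocol 8.3.1 collects all serious adverse events (SAEs) and adverse events of special interest (AESIs) to M6, and related SAEs and deaths to 5 years. Protocol 10.3.3 has both the Investigator and the Sponsor judge the relatedness of SAEs and non-serious AESIs. Protocol 6.3.2 keeps Investigators, the Sponsor, safety staff and participants blinded.

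**The concern.** The release of assignments is tied to an event, the end of the first interim analysis, and not to a date or to the completion of follow-up. Under the protocol's cut-off this did no harm to 6-month safety, because the interim could not close until every participant's M6 data were in. SAP 5.7 moves the event earlier but leaves the release tied to it. Neither document delays the listings, and neither separates the people who see unblinded data from the Sponsor staff who assess causality.

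At stake is the comparison of SAEs and AESIs between D29 and M6. Whether an event is reported, and whether it is called related, depends partly on judgement. An Investigator who knows that a participant received the new vaccine may decide differently from one who does not. Apart from this, SAP 5.4 and SAP 5.7 cannot both be followed, so the database lock that breaks the blind has two possible dates about five months apart.

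**Working it through.** The plan states no figure for this point, so there is none to reproduce. The check compares the texts and then works out the timing.

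**Texts.** Three places in the SAP bear on the cut-off. The Table 3.2 footnote and 5.7 say D29 for safety; 5.4 says M6, twice. All are current text. The release rule in protocol 2.3.2 names only the end of the first interim, so it follows whichever cut-off is used.

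**Inputs from the documents.** D29 sample: D29 to D35, using the +6-day analysis window (SAP Table 3.2 footnote, 5.1.1.1 and 5.7). M6 visit: D180 ± 15 days, so D165 to D195 (protocol Table 8.1). Planned enrolment: 570 (protocol 9.2).

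**Gap between one participant's D29 sample and M6 visit** = M6 day − D29 sample day.

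- Shortest: 165 − 35 = 130 days (4.3 months).
- Late D29 sample to nominal M6: 180 − 35 = 145 days (4.8 months).
- Longest: 195 − 29 = 166 days (5.5 months).

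For the last participant enrolled, this gap is the time available. Release comes before that participant's M6 visit only if assay, cleaning, lock and analysis together take less than this.

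**Share still before M6 at release.** Two quantities are not in the documents and are assumed: L, the lag in days from the last D29 visit (taken at D35) to release, and E, the length of enrolment in days, with participants entering uniformly. Then

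share = max(0, 180 − 35 − L) / E = max(0, 145 − L) / E, and number = 570 × share.

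| | E = 180 | E = 365 | E = 540 |
|---|---|---|---|
| L = 60 | 85/180 = 47% (269) | 85/365 = 23% (133) | 85/540 = 16% (90) |
| L = 90 | 55/180 = 31% (174) | 55/365 = 15% (86) | 55/540 = 10% (58) |
| L = 120 | 25/180 = 14% (79) | 25/365 = 7% (39) | 25/540 = 5% (26) |
| L ≥ 145 | 0 | 0 | 0 |

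Those affected are the participants vaccinated in the last 145 − L days of recruitment: 85 days at L = 60 and 25 days at L = 120. Each is exposed only from release to M6, at most the same number of days. The zero at L = 145 is for a nominal D180 visit. A last participant who comes at D195 stays exposed up to a lag of 195 − 35 = 160 days.

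**With an M6 cut-off, or with listings held until the last M6 contact,** the share is 0 whatever L and E are.

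**The case against.** A reader might infer that the SAP change does release assignments before 6-month follow-up ends, so that relatedness is judged unblinded across the trial. The documents do not support that. They give no release date and no lag, and a lag of about five months or more leaves nobody, or almost nobody, exposed. SAP 5.7 also reports that enrolment took longer than expected, which points toward the smaller shares in the table.

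Other points reduce the stakes:

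- Unblinded judgement of related SAEs after M6 is already part of the protocol under either cut-off, because they are collected to 5 years and the listings go out after the first interim.
- Observation for viscerotropic and neurologic events is concentrated in the 28 days after vaccination (protocol Table 2.1 and 10.3.6), which have passed by D29. AESIs count even when judged unrelated and are assessed against published case definitions (8.3.6).
- The sponsor's safety team and the independent data monitoring committee review safety throughout (9.5, 9.6).
- Participants learn their assignment only if they ask the site.
- The primary endpoint is little affected: the D29 samples are already drawn, and laboratory staff are blinded (8.1.2.2).

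A second tempting inference is that 6-month safety will be reported about half a year late. SAP 5.4 gives the Y1 interim whatever has not yet been analysed, so under 5.7 the M6 safety data would first appear there. But 5.4 also still places M6 safety in the interim study report. The documents leave the timing open.

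These points limit the size of the problem. They do not remove the contradiction, and none of them keeps the Investigator blinded to M6. Committee review does not blind causality assessment at the site, and case definitions do not settle whether an SAE is called related.

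**Conclusion.** The contradiction between SAP 5.4 and SAP 5.7 with Table 3.2 is certain and needs no assumption. It is equally clear that, with a D29 cut-off and protocol 2.3.2 unchanged, nothing guarantees that Investigators stay blinded until M6 follow-up is complete. Actual unblinding before M6 is a possibility, not an established fact. It needs a lag under about 130 to 166 days, it affects only later-enrolled participants, and it touches only events reported or assessed between release and their M6 contact. Under the assumed lags of 60 to 120 days and uniform enrolment over 180 to 540 days, about 5% to 47% of participants would be in that position; at 145 days or more, none at nominal D180. This should be corrected because the safeguard is simple and works whatever the lag turns out to be. It does not threaten the primary comparison.

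**What to change.** 1. Reconcile SAP 5.4, including its description of the interim study report, with SAP 5.7 and the Table 3.2 footnote, so that the first interim has one safety cut-off.
2. Amend protocol 2.3.2 so that individual listings go to Investigators only after the last participant's M6 contact is complete and the M6 safety data are locked.
3. State that, until then, unblinded individual data are also withheld from Sponsor staff who assess causality.
4. State which analysis first reports M6 safety.

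The SAP changes are wording only. The change to 2.3.2 is a protocol amendment and needs IRB/IEC approval before it takes effect (protocol 10.1.1). Participants would learn their assignment some months later. That matters to some extent, because 2.3.2 gives the two groups different information about certificates and travel, and exclusion E17 covers only travel to endemic countries already planned within 6 months of vaccination. Emergency code-breaking under protocol 6.3.2 is unchanged.

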Table 7.10: Abnormality and/or intensity for Biochemistry parameters measurements at D01and D11 – Subset
Table 7.11: Abnormality and/or intensity for Hematology parameters measurements at D01and D11 - Subset52
Table 7.12: Evolution of the intensity for Biochemistry parameters after vaccine injection - Subset 54
Table 7.13: Evolution of the intensity for Hematology parameters after vaccine injection – Subset

List of Figures

Figure 7.1: Reverse cumulative distribution curves for YF virus at each timepoint in participants with YF immune status at baseline - Microneutralization assays - Full Analysis Set	56
Figure 7.2: Reverse cumulative distribution curves for YF virus at each timepoint in participants with YF naive status at baseline - Microneutralization assays - Full Analysis Set	57
Figure 7.3: Reverse cumulative distribution curves for YF virus at each timepoint in participants with FV immune status at baseline - Microneutralization assays - Full Analysis Set	57
Figure 7.4: Reverse cumulative distribution curves for YF virus at each timepoint in participants with FV naive status at baseline - Microneutralization assays - Full Analysis Set:	57

 Table 7.1: Non-inferiority of the percentage of participants achieving seroconversion 28 days after one dose yellow fever vaccination in YF-naïve participants - Microneutralization assays - Per-Protocol Analysis Set

	vYFv			YF-VAX				
(N=xxx)			(N=xxx)			vYF – YF	Non-inferiority	
	Seroconversion rate			Seroconversion				
n/M	(%)	95% CI	n/M	rate (%)	95% CI	Difference (%)	95% CI	
###/###	##.#	(##.#; ##.#)	###/###	## . #	(##.#; ##.#)	##.#	(##.#, ##.#)	Yes/No

n: Number of participant s who achieve a yellow fever vaccination seroconversion.

M: Number of participant s with available data for the endpoint.

Seroconversion: for a participant with a fourfold increase in NAb titers as compared to the pre-vaccination value

The non-inferiority will be demonstrated if the lower limit of the 2-sided 95% CI is > -5%.

YF status			v' (N=	YF =###)		YF-V (N=#	AX ##)
	Time point/ratio	Μ	GM	(95% CI)	М	GM	(95% CI)
Immune	V01 (Pre-inj)	###	###.#	(###.#; ###.#)	###	###.#	(###.#; ###.#)
	V02 (V01+10d)*	###	###.#	(###.#; ###.#)	###	###.#	(###.#; ###.#)
	V04 (V01+28d)	###	###.#	(###.#; ###.#)	###	###.#	(###.#; ###.#)
	V05 (V01+6M)	###	###.#	(###.#; ###.#)	###	###.#	(###.#; ###.#)
	V06 (V01+1Y)	###	###.#	(###.#; ###.#)	###	###.#	(###.#; ###.#)
	V07 (V01+2Y)	###	###.#	(###.#; ###.#)	###	###.#	(###.#; ###.#)
	V08 (V01+3Y)	###	###.#	(###.#; ###.#)	###	###.#	(###.#; ###.#)
	V09 (V01+4Y)	###	###.#	(###.#; ###.#)	###	###.#	(###.#; ###.#)
	V10 (V01+5Y)	###	###.#	(###.#; ###.#)	###	###.#	(###.#; ###.#)
	Ratio V02 (V01+10d)/ V01 (Pre-inj)	###	###.#	(###.#; ###.#)	###	###.#	(###.#; ###.#)
	Ratio V04 (V01+28d)/ V01 (Pre-inj)	###	###.#	(###.#; ###.#)	###	###.#	(###.#; ###.#)
	Ratio V05 (V01+6M)/ V01 (Pre-inj)	###	###.#	(###.#; ###.#)	###	###.#	(###.#; ###.#)
	Ratio V06 (V01+1Y)/ V05 (V01+6M)	###	###.#	(###.#; ###.#)	###	###.#	(###.#; ###.#)
	Ratio V07 (V01+2Y)/ V06 (V01+1Y)	###	###.#	(###.#; ###.#)	###	###.#	(###.#; ###.#)
	Ratio V08 (V01+3Y)/ V07 (V01+2Y)	###	###.#	(###.#; ###.#)	###	###.#	(###.#; ###.#)
	Ratio V09 (V01+4Y)/ V08 (V01+3Y)	###	###.#	(###.#; ###.#)	###	###.#	(###.#; ###.#)
	Ratio V10 (V01+5Y)/ V09 (V01+4Y)	###	###.#	(###.#; ###.#)	###	###.#	(###.#; ###.#)
Naïve	•••						

Table 7.2: Summary of geometric means of titers and geometric means of individual titer ratios of antibody against YF virus by YF state	us at
baseline - Microneutralization assays - Full Analysis Set	

* Subset only

M: Number of participant s available for the endpoint

YF status: Immune for participants with quantified (\geq LLOQ) neutralizing Abs against YF; naive for participants without quantified (< LLOQ) neutralizing Abs against YF in the baseline sample

Sanofi Pasteur	
517 - vYF	

FV status			v (N=	YF =###)		YF-VAX (N=###)		
	Time point/ratio	Μ	GM	(95% CI)	Μ	GM	(95% CI)	
Immune	V01 (Pre-inj)	###	###.#	(###.#; ###.#)	###	###.#	(###.#; ###.#)	
	V02 (V01+10d)*	###	###.#	(###.#; ###.#)	###	###.#	(###.#; ###.#)	
	V04 (V01+28d)	###	###.#	(###.#; ###.#)	###	###.#	(###.#; ###.#)	
	V05 (V01+6M)	###	###.#	(###.#; ###.#)	###	###.#	(###.#; ###.#)	
	V06 (V01+1Y)	###	###.#	(###.#; ###.#)	###	###.#	(###.#; ###.#)	
	V07 (V01+2Y)	###	###.#	(###.#; ###.#)	###	###.#	(###.#; ###.#)	
	V08 (V01+3Y)	###	###.#	(###.#; ###.#)	###	###.#	(###.#; ###.#)	
	V09 (V01+4Y)	###	###.#	(###.#; ###.#)	###	###.#	(###.#; ###.#)	
	V10 (V01+5Y)	###	###.#	(###.#; ###.#)	###	###.#	(###.#; ###.#)	
	Ratio V02 (V01+10d)/ V01 (Pre-inj)	###	###.#	(###.#; ###.#)	###	###.#	(###.#; ###.#)	
	Ratio V04 (V01+28d)/ V01 (Pre-inj)	###	###.#	(###.#; ###.#)	###	###.#	(###.#; ###.#)	
	Ratio V05 (V01+6M)/ V01 (Pre-inj)	###	###.#	(###.#; ###.#)	###	###.#	(###.#; ###.#)	
	Ratio V06 (V01+1Y)/ V05 (V01+6M)	###	###.#	(###.#; ###.#)	###	###.#	(###.#; ###.#)	
	Ratio V07 (V01+2Y)/ V06 (V01+1Y)	###	###.#	(###.#; ###.#)	###	###.#	(###.#; ###.#)	
	Ratio V08 (V01+3Y)/ V07 (V01+2Y)	###	###.#	(###.#; ###.#)	###	###.#	(###.#; ###.#)	
	Ratio V09 (V01+4Y)/ V08 (V01+3Y)	###	###.#	(###.#; ###.#)	###	###.#	(###.#; ###.#)	
	Ratio V10 (V01+5Y)/ V09 (V01+4Y)	###	###.#	(###.#; ###.#)	###	###.#	(###.#; ###.#)	
Naïve								

Table 7.3: Summary of geometric means of titers and geometric means of individual titer ratios of antibody against YF virus by FV status at baseline - Microneutralization assays - Full Analysis Set

* Subset only

M: Number of participant s available for the endpoint

Flavivirus status: Immune for participants with quantified (\geq LLOQ) neutralizing Abs against YF, and/or against at least one dengue serotype, and/or Zika in the baseline sample; naive for participants without quantified (\leq LLOQ) neutralizing Abs against YF, with no Ab quantified against any of the four dengue serotypes and Zika in the baseline sample.

Table 7.4: Summary of percentages of participants achieving seroconversion after one dose YF vaccination by YF status at baseline - Microneutralization assays - Full Analysis Set

YF status Time point		vYFv (N=xxx)			YF-VAX (N=xxx)			
		Seroconversion rate			Seroconversion rate			
		n/M	(%)	95% CI	n/M	(%)	95% CI	
Immune	V02 (V01+10d)/ V01 (Pre-inj)	###/###	##.#	(##.#; ##.#)	###/###	##.#	(##.#; ##.#)	
	V04 (V01+28d)/ V01 (Pre-inj)	###/###	##.#	(##.#; ##.#)	###/###	##.#	(##.#; ##.#)	
	V05 (V01+6M)/ V01 (Pre-inj)	###/###	##.#	(##.#; ##.#)	###/###	##.#	(##.#; ##.#)	
	V06 (V01+1Y)/ V05 (V01+6M)	###/###	##.#	(##.#; ##.#)	###/###	##.#	(##.#; ##.#)	
	V07 (V01+2Y)/ V06 (V01+1Y)	###/###	##.#	(##.#; ##.#)	###/###	##.#	(##.#; ##.#)	
	V08 (V01+3Y)/ V07 (V01+2Y)	###/###	##.#	(##.#; ##.#)	###/###	##.#	(##.#; ##.#)	
	V09 (V01+4Y)/ V08 (V01+3Y)	###/###	##.#	(##.#; ##.#)	###/###	##.#	(##.#; ##.#)	
	V10 (V01+5Y)/ V09 (V01+4Y)	###/###	##.#	(##.#; ##.#)	###/###	##.#	(##.#; ##.#)	
Naive	•••						. , ,	

n: Number of participant s who achieve a yellow fever vaccination seroconversion.

M: Number of participant s with available data for the endpoint.

Seroconversion: For a participant with a fourfold increase in NAb titers as compared to the previous timepoint value

YF status: Immune for participants with quantified (\geq LLOQ) neutralizing Abs against YF; naive for participants without quantified (\leq LLOQ) neutralizing Abs against YF in the baseline sample.

Table 7.5: Summary of percentages of participants achieving seroconversion after one dose YF vaccination by FV status at baseline - Microneutralization assays - Full Analysis Set

FV status Time point		vYFv (N=xxx)			YF-VAX (N=xxx)			
		Seroconversion rate			Seroconversion rate			
		n/M	(%)	95% CI	n/M	(%)	95% CI	
Immune	V02 (V01+10d)/ V01 (Pre-inj)	###/###	##.#	(##.#; ##.#)	###/###	##.#	(##.#; ##.#)	
	V04 (V01+28d)/ V01 (Pre-inj)	###/###	##.#	(##.#; ##.#)	###/###	##.#	(##.#; ##.#)	
	V05 (V01+6M)/ V01 (Pre-inj)	###/###	##.#	(##.#; ##.#)	###/###	##.#	(##.#; ##.#)	
	V06 (V01+1Y)/ V05 (V01+6M)	###/###	##.#	(##.#; ##.#)	###/###	##.#	(##.#; ##.#)	
	V07 (V01+2Y)/ V06 (V01+1Y)	###/###	##.#	(##.#; ##.#)	###/###	##.#	(##.#; ##.#)	
	V08 (V01+3Y)/ V07 (V01+2Y)	###/###	##.#	(##.#; ##.#)	###/###	##.#	(##.#; ##.#)	
	V09 (V01+4Y)/ V08 (V01+3Y)	###/###	##.#	(##.#; ##.#)	###/###	##.#	(##.#; ##.#)	
	V10 (V01+5Y)/ V09 (V01+4Y)	###/###	##.#	(##.#; ##.#)	###/###	##.#	(##.#; ##.#)	
Naive	•••							

n: Number of participant s who achieve a yellow fever vaccination seroconversion.

M: Number of participant s with available data for the endpoint.

Seroconversion: For a participant with a fourfold increase in NAb titers as compared to the previous timepoint value

Flavivirus status: Immune for participants with quantified (\geq LLOQ) neutralizing Abs against YF, and/or against at least one dengue serotype, and/or Zika in the baseline sample; naive for participants without quantified (\leq LLOQ) neutralizing Abs against YF, with no Ab quantified against any of the four dengue serotypes and Zika in the baseline sample.

YF status	Time point	vYFv (N=xxx)			YF-VAX (N=xxx)		
		n/M	Seroprotection rate (%)	95% CI	n/M	Seroprotection rate (%)	95% CI
Immune	V01 (Pre-inj)	###/###	##.#	(##.#; ##.#)	###/###	##.#	(##.#; ##.#)
	V02 (V01+10d)*	###/###	##.#	(##.#; ##.#)	###/###	##.#	(##.#; ##.#)
	V04 (V01+28d)	###/###	##.#	(##.#; ##.#)	###/###	##.#	(##.#; ##.#)
	V05 (V01+6M)	###/###	##.#	(##.#; ##.#)	###/###	##.#	(##.#; ##.#)
	V06 (V01+1Y)	###/###	##.#	(##.#; ##.#)	###/###	##.#	(##.#; ##.#)
	V07 (V01+2Y)	###/###	##.#	(##.#; ##.#)	###/###	##.#	(##.#; ##.#)
	V08 (V01+3Y)	###/###	##.#	(##.#; ##.#)	###/###	##.#	(##.#; ##.#)
	V09 (V01+4Y)	###/###	##.#	(##.#; ##.#)	###/###	##.#	(##.#; ##.#)
	V10 (V01+5Y)	###/###	##.#	(##.#; ##.#)	###/###	##.#	(##.#; ##.#)
Naive	•••						

Table 7.6: Summary of percentages of participants achieving seroprotection after one dose YF vaccination by YF status at baseline -Microneutralization assays - Full Analysis Set

*Subset only.

n: Number of participant s who achieve a yellow fever vaccination seroprotection.

M: Number of participant s with available data for the endpoint.

Seroprotection: Participants with antibody titer $\ge 10 (1/dil)$

 $YF status: Immune for participants with quantified (\geq LLOQ) neutralizing Abs against YF; naive for participants without quantified (< LLOQ) neutralizing Abs against YF in the baseline sample.$

FV status	Time point	vYFv (N=xxx)			YF-VAX (N=xxx)		
		n/M	Seroprotection rate (%)	95% CI	n/M	Seroprotection rate (%)	95% CI
Immune	V01 (Pre-inj)	###/###	##.#	(##.#; ##.#)	###/###	##.#	(##.#; ##.#)
	V02 (V01+10d)*	###/###	##.#	(##.#; ##.#)	###/###	##.#	(##.#; ##.#)
	V04 (V01+28d)	###/###	##.#	(##.#; ##.#)	###/###	##.#	(##.#; ##.#)
	V05 (V01+6M)	###/###	##.#	(##.#; ##.#)	###/###	##.#	(##.#; ##.#)
	V06 (V01+1Y)	###/###	##.#	(##.#; ##.#)	###/###	##.#	(##.#; ##.#)
	V07 (V01+2Y)	###/###	##.#	(##.#; ##.#)	###/###	##.#	(##.#; ##.#)
	V08 (V01+3Y)	###/###	##.#	(##.#; ##.#)	###/###	##.#	(##.#; ##.#)
	V09 (V01+4Y)	###/###	##.#	(##.#; ##.#)	###/###	##.#	(##.#; ##.#)
	V10 (V01+5Y)	###/###	##.#	(##.#; ##.#)	###/###	##.#	(##.#; ##.#)
Naive	•••						

Table 7.7: Summary of percentages of participants achieving seroprotection after one dose YF vaccination by FV status at baseline -Microneutralization assays - Full Analysis Set

*Subset only.

n: Number of participant s who achieve a yellow fever vaccination seroprotection.

M: Number of participant s with available data for the endpoint.

Seroprotection: Participants with antibody titer ≥ 10 (1/dil)

Flavivirus status: Immune for participants with quantified (\geq LLOQ) neutralizing Abs against YF, and/or against at least one dengue serotype, and/or Zika in the baseline sample; naive for participants without quantified (\leq LLOQ) neutralizing Abs against YF, with no Ab quantified against any of the four dengue serotypes and Zika in the baseline sample.

Table 7.8: Safety overview affter a vaccine injection - Safety Analysis Set

¥¥	 	vYF			YF-VAX	
Period/		(N=###)			(N=###)	
Participants experiencing at least one:	n/M	%	(95% CI)	n/M	%	(95% CI)
Within 30 minutes after vaccine injection						
Immediate unsolicited AE	###/###	##.#	(##.# ; ##.#)	###/###	##.#	(##.# ; ##.#)
Immediate unsolicited AR	###/###	##.#	(##.#;##.#)	###/###	##.#	(##.#;##.#)
Solicited reaction within solicited period after vaccine injection	###/###	##.#	(##.#;##.#)	###/###	##.#	(##.#;##.#)
Solicited injection site reaction	###/###	##.#	(##.#;##.#)	###/###	##.#	(##.#; ##.#)
Solicited systemic reaction	###/###	##.#	(##.#;##.#)	###/###	##.#	(##.#;##.#)
Within 28 days after vaccine injection						
Unsolicited AE	###/###	##.#	(##.# ; ##.#)	###/###	##.#	(##.#; ##.#)
Unsolicited AR	###/###	##.#	(##.# ; ##.#)	###/###	##.#	(##.#; ##.#)
AE leading to study discontinuation	###/###	##.#	(##.# ; ##.#)	###/###	##.#	(##.# ; ##.#)
SAE	###/###	##.#	(##.# ; ##.#)	###/###	##.#	(##.# ; ##.#)
Death	###/###	##.#	(##.# ; ##.#)	###/###	##.#	(##.# ; ##.#)
Serious AESI						
Non-serious AESI	###/###	##.#	(##.# ; ##.#)	###/###	##.#	(##.# ; ##.#)
MAAE	###/###	##.#	(##.#;##.#)	###/###	##.#	(##.#;##.#)
During 6-month* follow-up period						
SAE	###/###	##.#	(##.# ; ##.#)	###/###	##.#	(##.# ; ##.#)
Death	###/###	##.#	(##.# ; ##.#)	###/###	##.#	(##.# ; ##.#)
Serious AESI	###/###	##.#	(##.# ; ##.#)	###/###	##.#	(##.# ; ##.#)
Non-serious AESI						
Serious MAAE	###/###	##.#	(##.#;##.#)	###/###	##.#	(##.#;##.#)
During the study						
SAE	###/###	##.#	(##.#;##.#)	###/###	##.#	(##.#; ##.#)
Related SAE						
Death	###/###	##.#	(##.#;##.#)	###/###	##.#	(##.# ; ##.#)
Serious related or fatal MAAE	###/###	##.#	(##.#;##.#)	###/###	##.#	(##.#; ##.#)

Confidential/Proprietary Information Page 47 of 57

Sanofi Pasteur
517 - vYF

n: number of participants experiencing the endpoint listed in the first column

M: number of participants with available data for the relevant endpoint

*During the period from 29 days after the injection until the last participant contact at M6

Table 7.9: Summary of solicited reactions within 7 or 14 days after a vaccine injection - Safety Analysis Set

		vYF (N=###)				X ¥)
Participants experiencing at least one:	n/M	%	(95% CI)	n/M	%	(95% CI)
Solicited reaction	###/###	###.#	(###.#; ###.#)	###/###	###.#	(###.#; ###.#)
Grade 3 solicited reaction	###/###	###.#	(###.#; ###.#)	###/###	###.#	(###.#; ###.#)
Solicited injection site reaction	###/###	###.#	(###.#; ###.#)	###/###	###.#	(###.#; ###.#)
Grade 3 injection site reaction	###/###	###.#	(###.#; ###.#)	###/###	###.#	(###.#; ###.#)
Solicited systemic reaction	###/###	###.#	(###.#; ###.#)	###/###	###.#	(###.#; ###.#)
Grade 3 systemic reaction	###/###	###.#	(###.#: ###.#)	###/###	###.#	(###.#: ###.#)

n: number of participants experiencing the endpoint listed in the first column

M: number of participants with available data for the relevant endpoint

		vYl (N=#	F ##)	YF-VAX (N=###)		
Parameter	Subject experiencing at least one abnormality at:	n/M	%	n/M	%	
Liver Function Tests – ALT increase by factor	V01 (Pre-inj)					
·	Intensity					
	Grade 1	###/###	#.#	###/###	#.#	
	Grade 2	###/###	#.#	###/###	#.#	
	Grade 3	###/###	#.#	###/###	#.#	
	Out of normal range	###/###	#.#	###/###	#.#	
	V02 (V01+10d)	•••				
Liver Function Tests – AST increase by factor						
Creatine phosphokinase (mg/dL)						
Alkaline phosphatase - increase by factor						
Bilirubin – when accompanied by any increase in Liver Function Test, increase by factor						
Bilirubin – when Liver Function Test is normal; increase by factor						
Creatinine (mg/dL)						

Table 7.10: Abnormality and/or intensity for Biochemistry parameters measurements at D01 and D11 – Subset

Sanofi Pasteur 517 - vYF					SAP Core Body for VY	7 F02
C-reactive protein	V01 (Pre-inj) Out of normal range	###/###	#.#	###/###	#.#	
	V02 (V01+10d) Out of normal range	###/###	#.#	###/###	#.#	

n: number of subjects experiencing the endpoint listed in the first column

M: number of subjects with available data for the relevant endpoint

		vYF (N=##	; #)	YF-VAX (N=###)		
Parameter	Subject experiencing at least one abnormality at:	n/M	%	n/M	%	
RBC (cell/mm ³)	V01 (Pre-inj)					
	Out of normal range	###/###	#.#	###/###	#.#	
	V02 (V01+10d)	•••				
Hematocrit (%)						
Mean corpuscular volume [MCV]						
Monocytes (cell/mm ³)						
Basophiles (cell/mm ³)						
Hemoglobin (gm/dL)	V01 (Pre-inj)					
	Intensity					
	Grade 1	###/###	#.#	###/###	# . #	
	Grade 2	###/###	#.#	###/###	#.#	
	Grade 3	###/###	#.#	###/###	#.#	
	Out of normal range	###/###	#.#	###/###	#.#	
	V02 (V01+10d)					
Hemoglobin change from baseline value						
WBC increase (cell/mm3)						

Table 7.11: Abnormality and/or intensity for Hematology parameters measurements at D01 and D11 - Subset

Decrease in WBC (cell/mm3)	
Decrease in Neutrophils (cell/mm ³)	
Decrease in Lymphocytes (cell/mm³)	
Eosinophils (cell/mm ³)	
Decrease in Platelets (cell/mm ³)	

				vY	F			YF-V	AX	
				(N=#	##)			(N=#	##)	
			Baseline				Base	ine		
			Grade 1	Grade 2	Grade 3	Total	Grade 1	Grade 2	Grade	3Total
Parameter	Visit	Intensity	n	n	n	n	n	n	n	n
Liver Function Tests – ALT increase by factor	V02 (V01+10d)	Grade 1	##	##	##	##	##	##	##	##
		Grade 2	##	##	##	##	##	##	##	##
		Grade 3	##	##	##	##	##	##	##	##
		Total	##	##	##	##	##	##	##	##
Liver Function Tests – AST increase by factor										
Creatine phosphokinase (mg/dL)										
Alkaline phosphatase - increase by factor										
Bilirubin – when accompanied by any increase in Liver Function Test, increase by factor										
Bilirubin – when Liver Function Test is normal; increase by factor										
Creatinine (mg/dL)										
										

Table 7.12: Evolution of the intensity for Biochemistry parameters after vaccine injection - Subset

n: number of subjects with available data for the relevant endpoint

				vY	F			YV-V	AX		
			(N=###)				(N=###) Baseline				
			Baseline								
			Grade 1	Grade 1 Grade 2 Grade 3 Total			Grade 1Grade 2Grade 3Total				
Parameter	Visit	Intensity	n	n	n	n	n	n	n	n	
Hemoglobin (gm/dL)	V02 (V01+10d)	Grade 1	##	##	##	##	##	##	##	##	
		Grade 2	##	##	##	##	##	##	##	##	
		Grade 3	##	##	##	##	##	##	##	##	
		Total	##	##	##	##	##	##	##	##	
WBC increase (cell/mm3)											
Decrease in WBC (cell/mm3)											
Decrease in Neutrophils (cell/mm ³)											
Decrease in Lymphocytes (cell/mm ³)											
Eosinophils (cell/mm ³)											
Decrease in Platelets (cell/mm ³)											
•••											

Table 7.13: Evolution of the intensity for Hematology parameters after vaccine injection – Subset

n: number of subjects with available data for the relevant endpoint

Sanofi	Pasteur	SAP Core Body for VYF02
517 - v	VF	

*Subset only.

<Instructions: This is a template, this will have 18 curves. The Y-axis represents percentage of participants having at least that level of serotype, and the scale is from 0% to 100%. The X axis represents the titers of the serotype.>

Confidential/Proprietary Information Page 56 of 57 <Label present in this order:

vYF: V01 (Pre-inj); vYF: V02 (V01+10d)*; vYF: V04 (V01+28d); vYF: V05 (V01+6M); vYF: V06 (V01+1Y); vYF: V07 (V01+2Y); vYF: V08 (V01+3Y); vYF: V09 (V01+4Y); vYF: V10 (V01+5Y) YF-VAX: V01 (Pre-inj); YF-VAX: V02 (V01+10d)*; YF-VAX: V04 (V01+28d); YF-VAX: V05 (V01+6M); YF-VAX: V06 (V01+1Y); YF-VAX: V07 (V01+2Y); YF-VAX: V08 (V01+3Y); YF-VAX: V08 (V01+3Y

Figure 7.2: Reverse cumulative distribution curves for YF virus at each timepoint in participants with YF naive status at baseline - Microneutralization assays - Full Analysis Set

*Subset only.

< Same shell as previous one>

Figure 7.3: Reverse cumulative distribution curves for YF virus at each timepoint in participants with FV immune status at baseline - Microneutralization assays - Full Analysis Set

*Subset only.

< Same shell as previous one>

Figure 7.4: Reverse cumulative distribution curves for YF virus at each timepoint in participants with FV naive status at baseline - Microneutralization assays - Full Analysis Set:

*Subset only.

< Same shell as previous one>
